## 6. DATA ANALYSIS

### 6.1 Model specification

Our main aim is to estimate the exposure-response relationship between prenatal and postnatal HAP exposures and severe pneumonia incidence during the first year of life. The unit of observation in this analysis is infant-quarter. Occurrence of HAPIN severe pneumonia is the primary endpoint.

We will use log-binomial regression to estimate a risk ratio for the association between  $PM_{2.5}$  exposure and severe infant pneumonia on any given quarter. Exposure-response relationships will be modelled as follows:

$$\log E(y_{ij}) = \beta_0 + f(X_{ij}) + \sum_{k=1}^m \gamma_k \times Z_{ij}$$

where  $y_{ij}$  is the presence or absence of a severe pneumonia episode for the  $i^{th}$  infant and in the  $j^{th}$  quarter. The function  $f(X_{ij})$  represents a range of functions to capture the relationship between HAPIN severe infant pneumonia rates and HAP exposures. We will consider different types of functions for  $f(X_{ij})$ , including linear and polynomials including regression splines, and functional smooths using generalized additive models (GAMs). We will conduct visual assessment of observed versus predicted values to assess goodness-of-fit and use metrics like the Akaike Information Criteria or Root Mean Squared Error to compare models. The  $Z_{ij}$  represent the  $m$  potential confounders (Section 5.2) some of which are fixed ( $Z_i$ ) and others time-dependent ( $Z_{ij}$ ). We will either use generalized estimating equations (GEE) with a compound symmetry matrix and a robust variance estimator to account for serial correlation by child or generalized linear mixed models with random effects to account for heterogeneity among children.

We will consider different functional forms for  $f(X_{ij})$  to model pollutant exposures ( $PM_{2.5}$  and CO) separately for prenatal and post-natal exposures, i.e.,  $f_{prenatal}(X_{ij}) + f_{post-natal}(X_{ij})$ . For prenatal exposures, we will use the mean of the mother's three pre-natal measurements (at baseline, at 24-28 weeks, and 32-36 weeks). Not all mothers had all three measurements, although most did. We will use all available measurements to calculate a mean. It is possible that the effect of pre-natal exposures wanes over time. We will compare goodness-of-fit between models that consider the average (power value of 0) and those at different power values (a decay at a power value of 1, 2 or 3).

As for post-natal values of  $X_{ij}$ , we will consider two approaches for measuring averages. The first will use means of values for  $\mathbf{X}$  for the  $j^{th}$  quarter using all values of personal exposures to  $PM_{2.5}$  that fall in the first quarter defined in Table 4, or the average of any prior exposures thereafter. We will consider unweighted means of the  $PM_{2.5}$  (or CO) exposures, and weighted mean of the values for  $\mathbf{X}$  considering the distances in time between the ages when personal exposures to  $PM_{2.5}$  were measured and the age at the start of the  $j^{th}$  quarter. The third approach uses a regression model to estimate infant's mean personal exposures. As children's data are missing for about 50% of post-natal measurements, we will use the mother's personal exposure measured at the same timepoint when the infant's measurement is missing. The unadjusted correlation of maternal and infant measurements is about 0.89. Prior work has shown that when using a regression model to predict time-specific infant exposures using mother's post-natal exposure and adjusted for season, weekend, and IRC, has correlation of 0.95 when compared with the infant's observed personal exposure. Using the assumption that maternal and child personal exposures measurements are similar, we anticipate that we will only have ~10% missing child exposure data. We will select the best approach for modeling exposure from the approach that leads to the least amount error in estimation of exposure (based on a root mean squared error in validation study).

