## **3.2. Analysis Populations**

The **exposure-response** analyses will include all follow-up time after birth and before death in study children whose households continue participating in HAPIN and who are at risk of a new severe pneumonia episode. No person-time is contributed to the cases of death of the mother prior to birth, miscarriage, stillbirth, and withdrawal from study prior to birth. Otherwise, person-time at risk was counted from the date of birth until the earliest date among the following: age 1 year, death of child, withdrawal from the study, or migration from the study area.

Missingness may affect exposure-response relationships. If the proportion missing exposure or confounder data is <10%, our study population for primary exposure-response analyses will be restricted to those

participants with complete data. If the proportion of exposure or confounder data missing is  $\geq 10\%$ , we will consider using multiple imputation methods to reduce missing data bias and loss of power.

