### 4.3. Withdrawal/follow-up

The study recorded reasons for exit classified into several categories:

- Not eligible
- Participant voluntary withdrawal
- Withdrawn by study team
- Moved away from study area (periods of intermittent moves outside study area will be excluded)
- Deceased
- Lost to follow up
- Mother abortion/miscarriage/stillbirth
- Child death
- Other

For exits due to eligibility, voluntary withdrawal and withdrawal by study team, several pre-specified reasons were used, as well as the option to fill in other reasons. The last completed visit was also recorded. Reasons for withdrawal and loss to follow-up were ascertained as soon as possible.

If reason for study exit is voluntary withdrawal

- Procedures too intrusive
- Procedures too time-consuming
- Do not see value in the study
- Family does not want me to participate
- Do not want to be in assigned group
- Other

If reason for study exit is withdrawn by study team:

- Repeated resistance to study procedures
- Danger to study personnel
- Other

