Mortality, n (%)	Binary	Death <30 days since diagnosis and/or Verbal Autopsy positive Yes/No

Children were permitted to meet the above case definition for severe pneumonia multiple times if the repeat event occurred either >14 days after the hospital discharge date or, if the hospital discharge data was not available or the child was not hospitalized, >30 days after the date the child met criteria for severe pneumonia. Implausible values and outliers identified from the variables that comprise the case definition will be considered missing. In addition to reporting the incidence rates of each endpoint, we will present the completeness of case ascertainment (e.g. proportion of reported healthcare visits with a screening, proportion of eligible cases with ultrasound assessment).

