**Table 4. Values of PM2.5 to use for exposure-response modeling.**

$t_{ij}$	Values for $X_{ij}$ (prenatal)*	Values for $X_{ij}$ (post-natal)
$t_{ij} \leq 3$		$X = \{PM_{2.5}(t = B1)\}$
$3 < t_{ij} \leq 6$		$X = \{PM_{2.5}(t = B1), PM_{2.5}(t = B2)\}$
$6 < t_{ij} \leq 12$	$X = \{PM_{2.5}(t = BL), PM_{2.5}(t = P1), PM_{2.5}(t = P2)\}$	$X = \{PM_{2.5}(t = B1), PM_{2.5}(t = B2), PM_{2.5}(t = B4)\}$

The error term for our regression model is a binomial distribution, and the canonical link is the logarithm function. Exponentiation of the difference between  $f(X_{ij})$  at different exposure values provides the risk ratio associated with that change in exposure. If we identify estimation problems when using the logarithm function, we will revert to use a logit function where exponentiation at different exposure values provides an odds ratio associated with that change in exposure. Since there are few cases (175 severe pneumonias) compared to the overall number of infant-quarters (~12,000), the odds ratio of a logistic regression should approximate the relative risk relatively well. We also do not expect zero-inflation to be a problem when using log or logit canonical links. The same log-linear (or logit) regression models will be used when using CO as the exposure, and in subgroup analyses and secondary outcomes, unless otherwise indicated.

*A priori* time-independent confounders will be crowding (number sleeping in house), IRC, SES, infant's sex and birthweight (or a z-score for birthweight for gestational age of child instead of birthweight). An SES score will be measured using a SES wealth index, but may also incorporate mother's education and nutrition data, and has been developed by our group and used in previous publications. *A priori* time-dependent confounders for the  $j^{\text{th}}$  quarter include age and season (winter or no), vaccination status, breastfeeding, and an indicator for pre vs post COVID-19 pandemic (i.e., 1 after March 15, 2020, and 0 otherwise).

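### The SAP defines person-time at risk, but the primary infant-quarter model has no time-at-risk term and no rule for partly observed quarters

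*SAP*

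**What the plan says.** Section 3.2 defines the exposure-response population by follow-up time in children at risk of a new severe pneumonia episode. It states that "person-time at risk was counted from the date of birth until the earliest date among the following": age 1 year, death, withdrawal or migration. Section 4.3 adds, on moves away, that "periods of intermittent moves outside study area will be excluded". Section 5.4, after Table 3, allows recurrence: "Children were permitted to meet the above case definition for severe pneumonia multiple times", provided the repeat comes more than 14 days after discharge or, without a discharge date or admission, more than 30 days after the case date. Earlier in 5.4, person-time is said to be treatable as continuous, weekly or intermittent. A quarterly format is not among these options.

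Section 6.1 gives the aim as "severe pneumonia incidence during the first year of life". It then says "The unit of observation in this analysis is infant-quarter" and that the outcome "is the presence or absence of a severe pneumonia episode for the" given infant and quarter. The model is introduced with "We will use log-binomial regression to estimate a risk ratio for the association between" exposure and outcome. The printed predictor contains an intercept, an exposure function and confounders. Within-child correlation is handled by GEE or random effects. A counting-process recurrent-event model is planned as secondary.

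**The concern.** The SAP specifies a denominator and then a primary model that does not use it. With a presence/absence outcome and no time-at-risk term, an infant who leaves one month into a quarter contributes the same event-free row as one observed for all three months. The model then estimates neither a rate, which the incidence aim implies, nor a clean three-month risk.

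If exit or absence is related to exposure beyond what the covariates capture, the exposure ratio is distorted. Treatment arm is the obvious candidate for such a link: it drives exposure, and section 5.2 says the primary analysis will not condition on it.

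Timing also matters. Section 5.1 already reports the overall event count, so an unwritten rule for partial quarters would be set with outcome data in hand. Section 6.2 gives the replicating analyst a cleaned dataset, so replication would not test a rule built into that dataset.

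**Working it through.** **Inputs from the SAP:** 2984 infants and 175 events (5.1); about 12,000 infant-quarters (6.1); 10% planned loss and 1440 per arm (2.3); 14- and 30-day repeat rules (5.4). **Assumed:** exit shares of 5%, 10% and 15%, uniform exit over the year, and the between-child frailty variance. The SAP gives no counts of exits, absences or repeat episodes.

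**1. The plan's own figures.** 2984 × 4 = 11,936, which matches the stated 12,000. The three age bands of Table 4 would give 2984 × 3 = 8,952, which does not. 175/2984 = 5.9% (stated 6%), and 1600 × 0.90 = 1440. Risk per infant-quarter is 175/11,936 = 1.47%.

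**2. Overcounted time.** With exit share d, person-quarters per infant are 4(1 − d/2). If the exit quarter counts as full and later quarters are dropped, as 3.2 requires, rows per infant are 4(1 − d) + 2.5d, because exit in quarter k leaves k rows and the mean of 1 to 4 is 2.5.
- d = 5%: 3.925/3.900, overcount 0.6%
- d = 10%: 3.850/3.800, overcount 1.3%
- d = 15%: 3.775/3.700, overcount 2.0%

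**3. Effect on the exposure ratio.**
- 5% versus 15% exit between exposure groups: (3.900/3.925)/(3.700/3.775) = 1.014, a shift of about 1.4%.
- Equal exit: 1.00.
- If all four rows were kept after exit, contrary to 3.2: 0.975/0.925 = 1.054.

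**4. Time not at risk after an episode.** At most 175 × 30/(2984 × 365) = 5,250/1,089,160 = 0.5% of follow-up.

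**5. Same-quarter repeats.** Expected number lost ≈ 11,936 × (0.01466²/2) × (1 + v) × ((91.3 − g)/91.3)², where g is the minimum gap in days and v the frailty variance.
- Independent episodes (v = 0): 0.9 for g = 14 and 0.6 for g = 30, about 1 of 175.
- Strong heterogeneity (v = 5): 5.5 and 3.5, or 2–3% of events.
- Only about 13–19% of repeat pairs fall in the same quarter, so most repeats stay in the model.

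**6. Scale.** If the 175 events split evenly between two exposure groups (assumed), the 95% interval extends by a factor of exp(1.96 × 2/√175) ≈ 1.34 in each direction. The shift in step 3 is small beside that.

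**The case against.** A discrete-time risk per quarter is a legitimate model, and at 1.5% risk it gives almost the same ratio as a rate model. IRC, SES and age are a priori covariates; with a log link, time at risk that varies with them is largely absorbed, so mere understatement of risk falls mainly on the intercept. The secondary counting-process model uses start and stop times and repeated events. All of this stands, and it keeps the expected distortion small. It does not supply the missing rule. The secondary model leaves the primary one unchanged, and its intervals are described by exposure-assessment dates rather than by exits or absences.

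Three stronger readings are tempting, and the SAP does not support them:

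- **That the model ignores repeat episodes.** Episodes in different quarters enter as separate positive rows. Only a second episode in the same quarter is lost.
- **That the SAP counts everyone as fully followed.** The phrase "compared to the overall number of infant-quarters (~12,000" is a rounded count inside a rare-outcome argument, not a declared denominator. With 5% exit and later quarters dropped, 2984 × 3.925 = 11,712, which also rounds to 12,000.
- **That the ratio could be off by about 5%.** That needs rows kept after exit, which 3.2 excludes. The 10% loss is also a planning value: it implies 2 × 1440 = 2880 infants, fewer than the 2984 reported.

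**Conclusion.** The point holds as a specification gap in the primary analysis. The person-time in 3.2 and 4.3 has no place in the 6.1 model, partial quarters have no rule, and same-quarter repeats are collapsed without the SAP saying so. The likely numerical effect is about 1% of counted time and about 1.4% on the ratio under a fairly marked difference in exit (5% versus 15%). It is nil if exit and absence are unrelated to exposure given IRC and SES. These sizes rest on assumed exit shares and uniform timing. They do not include absences, for which the SAP gives no figure. A change is worthwhile because it is cheap, matches the model to the stated aim and closes a choice that would otherwise be made after the events are known. No material bias has been shown.

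**What to change.** In 6.1, specify the primary model as a log-link Poisson regression of the number of episodes per infant-quarter. Use offset log(person-days at risk in that quarter), with person-days derived under 3.2 and 4.3 and the repeat-episode rule in 5.4, and a robust variance clustered on the child. Report a rate ratio. Quarters with no days at risk drop out. Choose one person-time format in 5.4 that agrees with this.

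This uses the SAP's own denominator and keeps same-quarter repeats. It also removes the need for the logit fallback in 6.1, which would change the effect measure to an odds ratio if the log-binomial model failed to fit. If the log-binomial model is kept, the SAP should at least state how partial quarters, absences and post-episode time are handled, and that same-quarter repeats count once.

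The cost is one derived variable, some SAP wording and a rate-ratio label in place of risk ratio. The two are nearly equal at about 1.5% risk per quarter.

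### The GEE option uses a compound-symmetry working correlation with a quarter-varying exposure, which adds a doubtful assumption for almost no precision; working independence avoids it, although the expected shift is small

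*SAP*

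**What the plan says.** Section 6.1 sets the data structure ("The unit of observation in this analysis is infant-quarter") and the model ("We will use log-binomial regression to estimate a risk ratio for the association between" PM2.5 and severe pneumonia). For repeated quarters on one child it offers two estimators without choosing. One is "generalized estimating equations (GEE) with a compound symmetry matrix and a robust variance estimator to account for serial correlation by child". The alternative is a mixed model in which each child has a random effect.

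Post-natal exposure varies by quarter. The text of 6.1 takes first-quarter readings, "or the average of any prior exposures thereafter". Table 4 uses nested sets: the 3-month reading (B1) up to 3 months, B1 and the 6-month reading (B2) up to 6 months, then B1, B2 and the 12-month reading (B4) from 6 to 12 months. For prenatal exposure, "we will use the mean of the mother's three pre-natal measurements", which is constant over quarters unless a decay is applied. Some confounders also vary by quarter, among them "vaccination status, breastfeeding, and an indicator for pre vs post COVID-19 pandemic".

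Section 2.7 gives each reading a length of 24 hours. Section 5.2 treats measurement error as a source of bias and gives true and measured exposure separate nodes in the causal diagram.

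**The concern.** Under compound symmetry, the estimating equations multiply one quarter's residual by the other quarters' covariates as well as its own. They have mean zero at the intended slope only if a child's risk in quarter j, given the modelled exposure for that quarter, does not depend on exposure values in other quarters. Working independence uses each residual only with its own quarter's covariates and needs no such condition. The robust variance corrects the standard error but not the value to which the estimate converges.

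The SAP neither states nor checks the condition, and its own view of exposure gives reason to doubt it. If true exposure drives risk and a 24-hour reading is a noisy proxy, B2 and B4 carry information about risk in the first quarter beyond what B1 gives. The GEE option could then estimate something other than the slope written in the 6.1 model. The same models are to be used for CO, subgroups and secondary outcomes.

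**Working it through.** **The plan's own figures.** 4 × 2984 infants = 11,936, which matches the stated ~12,000 infant-quarters. 175/2984 = 5.9%, which matches the stated 6%. Risk per quarter is 175/11,936 = 1.47%.

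**Assumptions, because the SAP gives no values.** Risk ratio 1.5 per SD of a single log reading (log 1.5 = 0.4055); reading reliability (ICC) 0.3 to 0.7; log-normal child frailty with variance v.

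**Plausible within-child correlation.** At this risk it is about 0.0149 × (exp(v) − 1): 0.004 at v = 0.25, 0.010 at 0.5, 0.026 at 1, 0.052 at 1.5 and 0.095 at 2. A correlation of 0.3 would need a risk of 0.0147 + 0.3 × 0.9853 = 31% in another given quarter after one event.

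**Large-sample slopes.** Log-link GEE, 300,000 children, four quarters, exposure as in Table 4, quarter indicators, outcomes replaced by their expected values:

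| What drives risk | ICC | Independence | CS, 0.01 | CS, 0.05 | CS, 0.10 | Change |
|---|---|---|---|---|---|---|
| Modelled mean | 0.3–0.7 | 0.4055 | 0.4055 | 0.4055 | 0.4055 | none |
| True long-run exposure | 0.3 | 0.1788 | 0.1778 | 0.1737 | 0.1684 | −0.6% to −5.8% |
| True long-run exposure | 0.5 | 0.2631 | 0.2622 | 0.2584 | 0.2533 | −0.3% to −3.7% |
| True long-run exposure | 0.7 | 0.3291 | 0.3285 | 0.3258 | 0.3223 | −0.2% to −2.1% |
| Current reading | 0.3 | 0.4054 | 0.4073 | 0.4148 | 0.4246 | +0.5% to +4.7% |
| Current reading | 0.5 | 0.4058 | 0.4070 | 0.4118 | 0.4182 | +0.3% to +3.1% |
| Current reading | 0.7 | 0.4054 | 0.4060 | 0.4087 | 0.4123 | +0.1% to +1.7% |

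(CS = compound symmetry at the working correlation shown.)

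**Hand check at ICC 0.3.** For a small, roughly constant risk, the slope is 0.4055 × (P − cQ)/(D − cE), with c = a/(1 + 3a) for working correlation a.

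- D is the sum of the four exposure variances: 1 + 0.65 + 0.5333 + 0.5333 = 2.7167.
- The four exposures sum to 2.1667 B1 + 1.1667 B2 + 0.6667 B4. The variance of that sum is E = 0.3 × 16 + 0.7 × 6.5 = 9.35.
- P is the sum of the same-quarter covariances between exposure and driver; Q is the covariance of the two four-quarter sums.
- Long-run driver: P = 4 × 0.3 = 1.2 and Q = 16 × 0.3 = 4.8. At a = 0, 1.2/2.7167 × 0.4055 = 0.179. At a = 0.10 (c = 0.0769), 0.8308/1.9974 × 0.4055 = 0.169, a change of −5.8%.
- Current-reading driver: P = 2.7167 and Q = 0.3 × 16 + 0.7 × 4.6667 = 8.0667. At a = 0.10, 2.0962/1.9974 × 0.4055 = 0.4255, a change of +4.9%.

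Both agree closely with the table.

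**At trial size.** 2984 children, 120 replicates per setting, ICC 0.3 and 0.6, v of 0.5 and 1.5, correlation estimated (means about 0.01 and 0.05). Mean shifts ran from −0.005 to +0.008 on the log scale. Mean robust standard errors were 0.084 to 0.097 under both structures and differed by at most 0.0003 (0.0970 against 0.0973, or 0.3%).

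**In standard errors (about 0.09).** The largest shift at correlation 0.05 is 0.4148 − 0.4054 = 0.0094, or 0.10 SE. At 0.10 it is 0.4246 − 0.4054 = 0.0192, or 0.21 SE.

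**The case against.** A reader might infer four stronger things, none of which the SAP supports.

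- **That compound symmetry is simply inconsistent here.** Nested readings alone do not make it so. If risk follows the modelled cumulative mean, both structures give 0.4055 at every correlation tried. A prenatal mean held constant over quarters is not itself subject to the problem.
- **That independence removes the bias.** It removes this source only. When long-run exposure drives risk, independence still converges to 0.18 to 0.33 against 0.4055, because of measurement error. That gap is far larger than any shift from the working correlation.
- **That the pull is towards the null.** It is when long-run exposure drives risk, and away from it when the current reading does.
- **That feedback from illness makes it much worse.** A simulated drop of 0.5 SD in exposure after an episode gave −5% to −12% under Table 4 but about zero with prior-only readings. The SAP gives no support for a drop of that size. Readings taken after an event are a separate timing problem, which independence does not cure because the quarter's own exposure would still contain them.

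It is also fair to say that compound symmetry with robust variance is a common choice, that the SAP may use the mixed model instead, and that with 175 events the estimated correlation will probably be close to zero. These points stand and make the matter minor. They do not supply a reason to prefer compound symmetry, which gains almost nothing in precision. Vaccination and breastfeeding raise the same question in principle, but the calculations varied only exposure, so no size is claimed for them.

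**Conclusion.** The point holds as a minor, conditional one. The GEE option rests on an assumption that the SAP does not state and that its own separation of true from measured exposure makes doubtful. If the assumption fails, the slope moves by about 0.3% to 6% at correlations of 0.01 to 0.10 with ICC 0.3 to 0.5, and by less at ICC 0.7. That is at most about 0.1 SE at a correlation of 0.05 and 0.2 SE at 0.10, in a direction that cannot be known in advance. It would rarely change a conclusion.

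The result rests on assumed values for the effect size, reading reliability and frailty variance. The SAP gives no within-child correlation, repeat-event count or reliability from which to fix them.

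**What to change.** In Section 6.1, state that if GEE is used, the working correlation is independence with robust variance clustered on child, and that compound symmetry, if fitted, is a sensitivity analysis. Because 6.1 carries the same models over to CO, subgroups and secondary outcomes, one edit covers them.

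The cost is one phrase and under about 1% in standard error (0.3% at most in the trial-size simulation). The choice between GEE and the mixed model, which makes its own assumption about the full exposure history, still has to be settled separately. So do attenuation from measurement error and the timing of readings relative to events.

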## **2.7. Timing of Outcome and Covariate Assessments**

Participating households were followed from enrollment until the index child reaches (or would have reached, assuming a live birth and continued vitality) their first birthday. For the purposes of this analysis plan, severe pneumonia follow-up is through the first year of life.

HAP exposure was assessed prenatally and postnatally. The measurement periods were 24 hours. Prenatal exposures include one measurement at baseline (<20 weeks, denoted as the BL measurement in our trial) and two post-randomization (at 24-28 weeks' gestation denoted as P1; and at 32-36 weeks' gestation denoted as P2). We measured child postnatal exposures indirectly as a reconstructed average of maternal personal exposures and two area concentrations three times at ages 3 (denoted as the B1 measurement), 6 (denoted as B2) and at 12 months (denoted as B4). A validation subset of 10% of participants had double the numbers of measures, with extra measures at time points spaced between those of the main study.

Time-invariant covariates that are potential confounders and effect modifiers were collected at baseline and birth. If effects of time-varying exposures are considered, covariates that could be time-varying confounders were collected at quarterly household visits during infancy (e.g. vaccination, breast feeding).

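### In quarter 1 the only post-natal exposure value is read at about 3 months, after most quarter-1 episodes; a companion analysis without quarter 1 should be pre-specified

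*SAP*

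**What the plan says.** All references are to the SAP.

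- Section 3.2: "person-time at risk was counted from the date of birth until the earliest date among the following" (age 1 year, death, withdrawal or migration). An episode at 0-3 months therefore counts.
- Section 6.1: "The unit of observation in this analysis is infant-quarter", and the outcome "is the presence or absence of a severe pneumonia episode for the" given infant and quarter.
- Section 2.7: the child's exposure was assessed "three times at ages 3 (denoted as the B1 measurement), 6 (denoted as B2) and at 12 months (denoted as B4". No earlier post-natal reading is scheduled for the whole cohort. A 10% validation subset had extra readings, which Table 4 does not use.
- Section 6.1: the post-natal value is the mean of readings "that fall in the first quarter defined in Table 4, or the average of any prior exposures thereafter".
- Table 4 agrees for the first quarter: its row for ages up to 3 months lists B1 alone.

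Prenatal exposure enters as a separate term, the mean of the BL, P1 and P2 readings, and does not replace the quarter-1 post-natal value.

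**The concern.** An exposure-response slope can be read as an effect of exposure only if the exposure value could not have been altered by the outcome. In quarter 1 the order is reversed for most surviving cases. A severe illness might change where the mother cooks, how much fuel is burned or who holds the infant, and B1 would then carry a trace of the illness. The quarter-1 slope would mix the effect of exposure on pneumonia with the effect of pneumonia on exposure.

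Nothing else in the plan would show this:

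- The exposure approach is chosen by root mean squared error against validation data. That measures how well exposure is estimated, not whether it depends on the outcome.
- Filling a missing infant value with the mother's reading from the same visit keeps the same timing.
- The first interval of the secondary Andersen-Gill model runs from birth to B1, so it has no earlier post-natal reading either.
- The sensitivity analyses in section 5.2 vary covariates only.

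The stated purpose is causal (sections 1.1 and 5.2), so the reader needs some indication of whether the slope depends on quarter 1.

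**Working it through.** **1. The plan's own figures.** 2984 infants x 4 = 11,936 infant-quarters, stated as about 12,000. 175/2984 = 5.86%, stated as 6%. 175/11,936 = 1.47% per infant-quarter. All reproduce; no stated figure is contested.

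**2. Timing.** Each reading's age (section 2.7) against the end of the period it serves:

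| Period (months) | Table 4 readings | At or after end of period | Same, under the section 6.1 text |
|---|---|---|---|
| 0-3 | B1 | 1 of 1 | 1 of 1 |
| 3-6 | B1, B2 | 1 of 2 (B2) | none |
| 6-9 | B1, B2, B4 | 1 of 3 (B4) | none |
| 9-12 | B1, B2, B4 | 1 of 3 (B4) | none |

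Quarter 1 is the only period in which text and table agree on a reading from the end of the period.

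**3. Size of the bias in quarter 1.** Assumptions, none from the documents: rare outcome, log-linear risk with slope beta per SD of true exposure, normal exposure, and a mean shift of -d SD in cases' readings, averaged over all cases. Then

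fitted quarter-1 slope = reliability x (beta - d), so the share lost is d/beta.

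- Risk ratio 1.5 per SD (beta = ln 1.5 = 0.405): d = 0.1, 0.2, 0.3 removes 25%, 49%, 74%.
- Risk ratio 1.3 (beta = 0.262): 38%, 76%, 114% (sign reversed).
- d = 0: nothing is lost. A rise in exposure (negative d) inflates the slope.

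A simulation of 4 million infants (reliability 0.4, risk ratio 1.5) gave slopes 0.161, 0.120, 0.084, 0.046 at d = 0, 0.1, 0.2, 0.3; the formula gives 0.162, 0.122, 0.082, 0.042.

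**4. What d means in households.** If a fraction f of case households lowers exposure by a proportion r, d = f x |ln(1 - r)| / SD of log exposure. With an assumed SD of 0.9, f = 25% and r = 30%, d = 0.25 x 0.357 / 0.9 = 0.10. With no true effect, that case gave a simulated quarter-1 risk ratio of 0.89 per log unit (0.84 at SD 0.7, 0.94 at SD 1.1).

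**5. Pooled over the year.** If 25-40% of events fall in quarter 1 (assumed) and later quarters are unaffected, the loss at risk ratio 1.5 is 0.25 to 0.40 x 25% = 6-10% at d = 0.1, and 0.25 to 0.40 x 74% = 18-30% at d = 0.3. A full-year simulation (events spread evenly, SD 0.9, true risk ratio 1.20 per log unit, no measurement error) gave:

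| f, r | Text's rule | Earlier readings only, no quarter 1 |
|---|---|---|
| 25%, 30% | 1.17 | 1.20 |
| 50%, 30% | 1.13 | 1.20 |
| 50%, 50% | 1.08 | 1.19 |

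**6. Price of leaving quarter 1 out.** 25-40% of 175 is about 44-70 events. The standard error grows by 1/sqrt(0.75) = 1.15 to 1/sqrt(0.60) = 1.29. With reliability 0.4 the SD of measured exposure is sqrt(1/0.4) = 1.58, so the standard error is 1/(sqrt(175) x 1.58) = 0.048 with all events and 0.055-0.062 without quarter 1.

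**7. Total error.** Pooled bias = 0.4 x d x share. Root mean squared error = sqrt(bias^2 + SE^2):

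| d | Four-quarter model | Quarters 2-4 only |
|---|---|---|
| 0.1 | 0.049-0.050 | 0.055-0.062 |
| 0.2 | 0.052-0.058 | 0.055-0.062 |
| 0.3 | 0.056-0.068 | 0.055-0.062 |

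**The case against.** The strongest reply is that the harm is hypothetical. The documents report no change in cooking or infant care after an episode, nor that a change would still show in a 24-hour reading weeks later. The risk ratio, d, the reliability and the quarter-1 share are all assumed. About half of the infant readings are missing and the mother's reading stands in, so a change in who holds the infant would not move those values. Visit windows are not given, so some quarter-1 episodes may follow B1. No earlier scheduled reading exists for the whole cohort, so this is a limit of completed data collection.

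All of this stands, and it governs what can be claimed and asked for. It does not restore the time order, and a change in the mother's own cooking would still move her reading.

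Three stronger readings may tempt a reader, and the documents do not support them:

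- *The bias runs towards no effect.* Its sign depends on whether exposure falls or rises after illness, and nothing in the SAP favours either. If there is no true effect, a fall produces a spuriously protective slope, which is away from the null.
- *The plan keeps time order everywhere except quarter 1.* That is true of the section 6.1 text but not of Table 4, whose later rows include B2 and B4. That conflict is a separate matter to reconcile.
- *The lead model should drop quarter 1, or use P2 in its place.* By step 7, dropping it gives larger total error at d = 0.1 and 0.2. P2 is already part of the prenatal mean, so using it again as a post-natal value would blur two terms that the plan keeps apart.

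**Conclusion.** The timing is established from the SAP alone: in quarter 1 the only post-natal value is read at about 3 months, after the episode for most surviving cases, and the rule for earlier readings begins only afterwards. That the slope is biased is not established. The bias is downward if exposure falls after illness, upward if it rises and zero if behaviour is unchanged. The SAP gives no data on which applies, and every magnitude above is illustrative.

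This justifies a pre-specified sensitivity analysis, not a new lead model. The check has limited power. Under the assumptions of steps 6 and 7, the difference between the two slopes has a standard error of sqrt(0.055^2 - 0.048^2) = about 0.03 to sqrt(0.062^2 - 0.048^2) = about 0.04. The expected difference is 0.4 x 0.1 x (0.25 to 0.40) = 0.010-0.016 at d = 0.1, and 0.030-0.048 at d = 0.3. Agreement would therefore rule out only large shifts. A gap could also reflect chance or a different effect at the youngest ages (child age is a listed modifier in Table 5), so it would call for a caveat and would not prove reverse order.

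**What to change.** In section 6.1, keep the B1-based four-quarter model as lead and add one pre-specified sensitivity analysis:

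- Estimate the post-natal slope from quarters 2-4, using only readings dated before the quarter starts, by the same rule for cases and non-cases.
- State that an infant-quarter with no such reading (for example quarter 2 when B1 was taken late) does not contribute to the post-natal slope, whatever its outcome.
- Report the estimate beside the lead one. State that if they differ materially, the post-natal slope will not be read as causal without that caveat.
- Do not use P2 as a quarter-1 post-natal stand-in.

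The later rows of Table 4 should be reconciled with the text first; otherwise the comparison also picks up the B2 and B4 readings.

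The cost is some SAP wording and one more fit on data in hand. The companion interval would be about 15-29% wider if 25-40% of events fall in quarter 1, and wider still if many B1 visits fall after the start of quarter 2.
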